Structured Interview Guide for the Hamilton Depression Rating Scale (SIGH-D)⁸⁹: The SIGH-D is a 17-item clinician-administered measure of overall severity of depressive symptoms in the past week.

The following self-report measures will also be administered at the clinical assessment visits (baseline, mid-treatment, post-treatment, and 3-month follow-up) to assess OCD, GAD, and depression symptom severity respectively:

Dimensional Obsessive-Compulsive Scale (DOCS)⁹⁰: The DOCS assesses the symptom severity of the following four OCD symptom dimensions: (a) concerns about germs and

contamination, (b) responsibility for harm, injury, or bad luck, (c) unacceptable thoughts, and (d) concerns about symmetry, completeness and need for things to be “just right”.

State Trait Anxiety Inventory-Trait (STAI-T)⁹¹: The STAI-T is a 20-item questionnaire of trait anxiety in which respondents are asked to rate the intensity of their feelings in general (e.g., “I am tense”).

Beck Depression Inventory (BDI-II)⁹²: This 21-item self-report inventory is a widely used measure of depression severity that assesses the affective, cognitive, motivational, vegetative, and psychomotor components of depression.

Clinical Global Impression Scale – Severity and Impairment (CGI-S/I)⁹³: The CGI-Severity (CGI-S) is a measure of the global severity of symptoms. It ranges from 1 (normal, not ill at all) to 7 (among the most extremely ill patients) and is commonly used in clinical trials. The CGI-S will be administered by the IE at the clinical assessment visits (baseline, mid-treatment, post-treatment, and 3-month follow-up).

The CGI-Improvement (CGI-I) is a global rating scale of improvement during treatment that ranges from 1 (very much improved) to 7 (very much worse). Subjects will complete a CGI-I for RNT symptoms (CGI-RNT) and for overall anxiety, mood, and mental health symptoms (CGI-Global) at each therapy visit, at mid-treatment, post-treatment, and at 3-month follow-up. The IE will complete the CGI-RNT and CGI-Global at the following assessment visits: mid-treatment, post-treatment, and 3-month follow-up. The CGI-I will be used to determine whether subjects experience clinical deterioration and should be withdrawn from the study (see section on “Participant Withdrawal” below).

Functioning and Quality of Life

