Work and Social Adjustment Scale (WSAS)⁹⁴ The WSAS is a 5-item self-report scale assessing disability in work, home management, social leisure activities, private leisure activities, and the ability to form and maintain close relationships, each on 8-point scales. A composite score can be calculated by summing the five scales for a dimensional measure of global functional impairment that ranges from 0 to 40, in which higher scores denote greater disability. Specifically, WSAS total scores less than 15 indicate mild disability, between 15 and 30 moderate disability, and greater than 30 severe disability. The WSAS will be administered at screening to determine eligibility (moderate impairment of RNT; WSAS total score ≥ 15 and ≥ 4 on any of the 5 sub-scales) and at the clinical assessment visits (baseline *if more than 7 days has passed since screening*, mid-treatment, post-treatment, and 3-month follow-up).

Quality of Life Enjoyment and Satisfaction Questionnaire – Short Form (Q-LES-Q-SF)⁹⁵: The Q-LES-Q-SF is a 16-item self-report measure of quality of life, often used in treatment studies, that focuses on social relationships, emotional well-being, physical health, leisure activities, work, school, and household duties. The Q-LES-Q-SF will be administered at the clinical assessment visits (baseline, mid-treatment, post-treatment, and 3-month follow-up).

Assessment of Safety, Concomitant Treatment, and Adverse Events

Beck Depression Inventory (BDI-II) – Suicide Item⁹²: Item #9 of the BDI-II regarding suicidal thoughts or wishes will be given at screening to determine eligibility (scores ≥ 2 are exclusionary, “2 - I would like to kill myself” and “3 - I would kill myself if I had the chance”). This item also will be administered weekly to monitor suicidal ideation.

Concomitant Medication (CMED) Log: The RA will administer the CMED form at the clinical assessment visits (baseline, mid-treatment, post-treatment, and 3-month follow-up) and before each therapy session to probe for any changes in medications for mood, anxiety, sleep, or other psychological symptoms that may have occurred since the last session. Changes in psychotropic medications or dose are not allowed during the study. At each visit, the research coordinator will update the CMED Log to track all psychotropic medications, including dose. The therapist will review the completed CMED Log before each therapy session.

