6. BIOSTATISTICAL ANALYSIS

Overview

Data acquisition and analytics approaches will be performed by [name] under the supervision of biostatistician [name]. To characterize our sample, data will be displayed graphically, and summary statistics (e.g., means and frequencies) will be calculated for all variables, including demographic and clinical descriptors. Descriptive statistics and exploratory graphing (e.g., scatter plots) will be used to assess normality, skew, and outliers on all measures. Continuous measures will be transformed if necessary, to satisfy assumptions of normality and homogeneity of variance.

Baseline differences between the treatment arms (AR-ERT vs. SPT) in demographic and other potential prognostic variables will be examined using chi-square analyses for discrete variables and ANOVA for continuous variables. While randomization tends to produce well-balanced treatment samples, if we find significant differences in potentially important baseline variables, we will include these variables as covariates in subsequent multivariate analyses. Candidate covariates for adjustment include baseline values of RNT (PTQ-PW score), symptom measures (Y-BOCS, SIGH-A, SIGH-D), and use of psychotropic medication (yes/no). Additional covariates that are unlikely to moderate treatment effect, but nonetheless will be examined for completeness, include: age, gender, education, race/ethnicity (majority vs. minority as we do not anticipate recruiting enough subjects from any one minority group to perform analyses for specific groups). If effects of gender and/or minority status are found that might be clinically meaningful, even if not statistically significant, we will report these to guide future research. Frequencies of adverse events (with 95% confidence intervals) will be calculated by treatment arm and type of event. We also will compare treatment groups on baseline credibility/expectancy of treatment and post-treatment satisfaction. A two-tailed p value $<.05$ will be considered evidence of statistical significance for the primary outcome.

Missing Data

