- 2) **Electrophysiological:** (a) proactive cognitive control in anticipation of conflict (i.e., cue-locked N2 ERP amplitudes on “opposite” vs. “actual” trials; CECT), and (b) reactive cognitive control in response to conflict (i.e., target-locked N2, N450, and P300 ERP amplitudes after the “opposite” vs. “actual” cue; CECT),
- 3) **Self-report:** Attentional Control Scale (ACS).

We will analyze each target index individually without adjusting for multiple testing¹²⁸ in order to be inclusive in identifying targets for future studies (e.g., R61/R33 proposal). Analyses will be modeled as the GLM equivalent of 2 x 3 ANOVAs with treatment condition (AR-ERT vs. SPT), time (pre-, mid-, post-treatment), and their interaction as fixed effects; the primary contrast of interest will be treatment difference at week 8 (post-treatment).¹²⁹ Repeated measures per person will be modeled with either an auto-correlation, Toeplitz, or unstructured covariance matrix (choosing the best model based on AIC and BIC).

Hypothesis 2a: Treatment Efficacy. To examine whether repetitive negative thinking (RNT) and psychiatric functioning improve during AR-ERT, we will also use GLM. Analyses will be modeled as the GLM equivalent of 2 x 4 ANOVAs with treatment condition (AR-ERT vs. SPT), time (pre-, mid-, post-treatment, follow-up), and their interaction as fixed effects; the primary contrast of interest will be treatment difference at week 8 (post-treatment), and a secondary outcome contrast will be at week 20 (3-month follow-up). Outcomes include:

- 1) **Repetitive Negative Thinking:** (a) Perseverative Thinking Questionnaire – Past Week (PTQ-PW; primary outcome), (b) Rumination Response Scale (RRS), (c) Penn State Worry Questionnaire (PSWQ), and (d) Rumination on Obsessions and Compulsions Scale (ROCS).

- 2) **Clinical Symptoms:** (a) Yale-Brown Obsessive Compulsive Scale (Y-BOCS) and Dimensional Obsessive-Compulsive Scale (DOCS), (b) Structured Interview Guide for the Hamilton Anxiety Rating Scale (SIGH-A) and State Trait Anxiety Inventory-Trait (STAI-T), (c) Structured Interview Guide for the Hamilton Depression Rating Scale (SIGH-D) and Beck Depression Inventory (BDI-II), and (d) Clinical Global Impression Scale – Severity (CGI-S).
- 3) **Psychiatric Functioning:** (a) Work and Social Adjustment Scale (WSAS), and (b) Quality of Life Enjoyment and Satisfaction Questionnaire – Short Form (Q-LES-Q-SF).

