7. RISKS AND DISCOMFORTS

The following are potential risks/discomforts that participants may experience in this study:

- 1) **Assessments and Questionnaires.** During the study assessments, participants may feel bored or tired completing some of the questionnaires or computer tasks. They also might experience some discomfort, embarrassment, or anxiety from discussing personal material and completing self-report questionnaires. Likewise, some participants may feel uncomfortable about having assessment sessions digitally recorded and reviewed by study staff (which is necessary for rater supervision as well as assessment of the reliability of ratings).
- 2) **EEG.** There are no known or foreseeable risks or side effects associated the EEG procedures. The EEG sensors (Brain Products GmbH, Gilching, Germany) have been approved by the U.S. Food and Drug Administration (FDA) for research purposes and will be operated within the standards reviewed and accepted by the FDA. Participants may experience some discomfort because we may have to gently scrape the skin in order to receive clear signals from the EEG electrodes.
- 3) **Computer tasks.** Some of the scenes that participants will view during the Emotional Interference Task (EIT) involve emotionally evocative images of violence, death, blood/gore, and sex (from the International Affective Picture System [IAPS] dataset) and may generate distress.
- 4) **Treatment.** The treatment offered in this study may make some individuals temporarily distressed during procedures that involve confronting the content of their repetitive negative thoughts and associated emotions of depression and anxiety (e.g., mindfulness of thoughts and emotions; imaginal rehearsal tasks); however, these procedures rarely make subjects significantly distressed, and participants will be able to manage the intensity of these exercises along with their therapist. Participants may also experience an increase in distress due to the natural waxing and waning of OCD, anxiety, and depression symptoms; however, participants will be carefully monitored, and measures will be taken to minimize potential risks during the project period (as discussed in "Protection Against Risks" below).

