 - i) Any data that is shared with other collaborators in the future would only be done so after executing a formal Data Use Agreement from Massachusetts General Hospital (MGH). As part of this process, the final dataset would be stripped of any identifiers that would permit linkages to individual research participants prior to release for sharing (i.e., coded). Additionally, given the sensitive nature of psychiatric symptoms and diagnosis and our relatively small sample size, we would make the data and associated documentation available to users only under a data-sharing agreement that provides for: (1) a well-described justification for the use of the data; (2) a commitment to using the data only for research purposes (under purview of an institutional IRB) and not to identify any individual participant; (3) a commitment to securing the data using appropriate computer technology; (4) a commitment to not transfer the data to other users; and (5) a commitment to destroying the data after analyses are completed. In compliance with NIH guidelines, data sharing would be done in a timely fashion (i.e., no later than the acceptance for publication of the main findings for the final dataset).
 - j) Due to the NIH-funding for this study, a Certificate of Confidentiality will automatically be obtained.
 - k) All necessary precautions will be taken to ensure participant privacy while conducting virtual study visits over ZoomTM. Healthcare Secure ZoomTM includes built in protections such as chat encryption, mandatory waiting rooms, and disablement of video recordings.
- 6) Emergencies and Suicidality.** Because patients with affective disorders can also experience suicidal thinking and behaviors, we will carefully implement safety precautions including:
- a) Patients who are actively suicidal at the screening visit (as assessed by the SCID-5-RV, SIGH-D, and/or score on the BDI-II suicide item #9 ≥ 2) will be excluded from the study.
 - b) Screening procedures will also exclude any individuals at potentially greater risk for psychiatric deterioration or an adverse outcome, or who are not clinically suitable for the study protocol. For example, as described in the

inclusion/exclusion criteria above, individuals will be excluded if they have active and clinically significant homicidality or any features requiring a higher level of care.

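### Weekly suicide-item scores and weekly patient ratings of worsening have no by-arm summary, so a patient who worsens, stays in the study and has no adverse event logged is counted in no named analysis

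*Combined protocol and SAP*

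**What the plan says.** **Collection.** Section 5 (safety assessments) gives BDI-II item 9 at screening and then weekly: "This item also will be administered weekly to monitor suicidal ideation". Table 1 lists it under Safety. For the global rating, section 5 (Symptom Measures) says: "Subjects will complete a CGI-I for RNT symptoms (CGI-RNT) and for overall anxiety, mood, and mental health symptoms (CGI-Global) at each therapy visit". Its stated use is individual: "The CGI-I will be used to determine whether subjects experience clinical deterioration and should be withdrawn from the study".

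**Why these are watched.** Section 7 states that "The treatment offered in this study may make some individuals temporarily distressed during procedures that involve confronting the content of their repetitive negative thoughts", and also that "Participants may also experience an increase in distress due to the natural waxing and waning of OCD, anxiety, and depression symptoms". The emergency and suicidality safeguards are introduced with "Because patients with affective disorders can also experience suicidal thinking and behaviors".

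**Individual rules.** Participant Withdrawal in section 7 names an item 9 score of 2 or more followed by evaluation by the investigator. It also names a CGI-I of 6 or 7 for three consecutive weeks together with therapist and investigator judgment, and allows earlier withdrawal on judgment.

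**Analysis.** The Overview of section 6 plans: "Frequencies of adverse events (with 95% confidence intervals) will be calculated by treatment arm and type of event". Missing Data in section 6 commits to examining the reasons for dropout and withdrawal by treatment group. Hypothesis 2a models the BDI-II, SIGH-D, CGI-S and other scales at pre-, mid- and post-treatment and follow-up. Neither item 9 as a separate variable nor the CGI-I is on that list. Section 9 has a DSMB that reviews group-level data on key outcomes, which it does not name, and adverse events twice a year.

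**The concern.** The trial collects two structured weekly self-reports aimed at the harms it anticipates, and the analysis section uses neither to compare the arms. An adverse-event table depends on someone recognising and logging an event. A weekly score is recorded on a fixed schedule in both arms, whatever the therapist or research assistant judges to be an event. That matters here because the AE Form is given at therapy sessions by the therapist, who knows the arm.

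At stake is what the report can say about harm. The arms could differ in how many patients had emergent suicidal ideation or rated themselves much worse, and the planned outputs need not show it. If the summary is not specified in advance, the definition of worsening would also be chosen after the data are seen.

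**Working it through.** **1. Denominators.** The plan states no figure for these safety data. Its sample-size figures reproduce: 52 / 0.85 = 61.2, so 62 enrolled; 62 / 2 = 31 per arm and 52 / 2 = 26 completers per arm. A two-sample t-test with 26 per arm, effect size 0.8 and two-sided 0.05 has power 80.7%, against 80% stated. That power concerns the efficacy contrast only.

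**2. Tracing one patient through the planned outputs.** Take a patient who scores item 9 of 2, or CGI-I of 6, in one week between assessments, is judged safe to continue, and completes the trial.
- Adverse-event table: included only if an event is logged. Nothing in the document makes item 9 of 2 or more, or CGI-I of 6 or 7, an adverse event.
- Withdrawal reasons by arm: not included, because the patient was not withdrawn.
- Hypothesis 2a models: the weekly score is not an input. At assessment visits item 9 enters only as one of the 21 items in the BDI-II total, and the CGI-I does not enter.
- DSMB review: not assured, because the key outcomes are not named.

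**3. How much stricter the withdrawal rule is than any worsening.** Assume a chance w of a CGI-I of 6 or 7 each week, independent over 8 weeks. P(at least one such week) = 1 - (1 - w)^8. P(three consecutive such weeks) comes from simulating 400,000 patients.

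| w (assumed) | At least one week | Three consecutive weeks |
|---|---|---|
| 5% | 34% | 0.07% |
| 10% | 57% | 0.6% |
| 20% | 83% | 3.9% |

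Real ratings are correlated within a patient, so the gap would be smaller, but the three-week criterion stays much the stricter. Because earlier withdrawal on judgment is allowed, these are not withdrawal rates.

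**4. Why arm means do not substitute.** Assume 10% worsen by 1 SD and 90% improve by 1 SD: 0.90 × (-1) + 0.10 × (+1) = -0.80 SD, still a large mean improvement. With 15% worsening: 0.85 × (-1) + 0.15 × (+1) = -0.70 SD.

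**5. What the added table could show with 31 per arm.** Counts are assumed. Per-arm intervals are exact (Clopper-Pearson) and differences are Newcombe.
- 0/31: upper limit 1 - 0.025^(1/31) = 11.2%.
- 3/31 = 9.7%: 2.0% to 25.8%.
- 4/31 versus 1/31: 12.9% - 3.2% = 9.7 points (-5.4 to 25.8), Fisher p = 0.35.
- 6/31 versus 1/31: 19.4% - 3.2% = 16.1 points (-0.4 to 33.3), Fisher p = 0.10.
- For 80% power against a control rate of 5%, the other arm would need about 32.5% (normal approximation).

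**The case against.** The strongest reply is that much of this ground is already covered.
- Section 9 lists a passing rise in anxiety or depression as an expected adverse event, and such events are tabulated by arm.
- Withdrawal reasons are examined by arm, and they include active suicidal ideation, the item 9 trigger and the CGI-I trigger.
- Event capture does not rest on the therapist alone. The research assistant gives the form at assessment visits, clinicians ask about suicidality at each visit, and the investigator reviews events weekly.
- A DSMB sees group-level data.
- In a pilot of 62, a table this imprecise could rarely separate the arms.

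All of that stands, and it narrows the point. It does not reach the patient who crosses a threshold, is retained and has no event logged. Section 5 also offers up to two additional sessions for crises with retention as their aim, so such patients are plausible. The Overview's summary statistics for all variables are meant to characterise the sample; they are not stated to be by arm and define no worsening event.

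A reader might infer more than the documents support:
- That adverse events are the only safety analysis, or that the weekly scores never reach a comparison by arm. The withdrawal analysis contradicts both.
- That patients are unprotected. Individual monitoring and withdrawal rules are in place; the gap is in analysis and reporting.
- That AR-ERT is known to cause deterioration or suicidality. Section 7 speaks of temporary distress that is rarely significant, and links suicidal thinking to the patient population.
- That the risk-benefit statement in section 8 would rest on incomplete results. It is a prospective statement made before any data.

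**Conclusion.** The point holds as a reporting gap of modest size. Weekly item 9 and patient CGI-I scores have no by-arm summary in section 6, and scores between assessment visits enter no model. The unreported group is limited to patients who cross a threshold, remain in the study and have no adverse event logged. Its size cannot be derived, because the documents give no rates; every event count and weekly probability in the working is an assumption. The omission itself rests on the text alone. Up to 8 weekly scores per patient, or 8 × 31 = 248 per arm for each measure, would otherwise go without a specified comparison. The change is worth making because it affects what the trial can say about harm. With about 31 per arm it supports description only.

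**What to change.** Add one table to the Overview of section 6, labelled descriptive, by randomised arm among all randomised patients, giving the number and percentage with:
1. any post-baseline item 9 score of 2 or more, from the weekly items and the full BDI-II at assessment visits. The week-0 BDI-II serves as baseline, since Table 1 has no separate baseline entry for item 9;
2. any patient CGI-I of 6 or 7 and, separately, three consecutive such weeks. Show CGI-RNT and CGI-Global separately, because the withdrawal text does not say which of them applies.

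Give exact 95% confidence intervals per arm, a confidence interval for the difference, and the number of weekly scores available per arm, so that unequal completion is visible. Include the table in the DSMB report. Cross-refer to the existing analysis of withdrawal reasons rather than repeating it.

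The score levels are those already in section 7. Counting a single week of CGI-I 6 or 7 is a reporting category added here; it is not a withdrawal criterion, and no clinical rule changes.

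The cost is one table from data already collected, with no change to sample size or visits. The 3-month BDI-II responses are held in a separate system (section 9, Data Management), so item 9 at that visit must be exported from there. The drawback is wide intervals: no formal test should be attached, and a table with few or no events should not be read as evidence of no harm.

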Attentional Control Scale (ACS)³³: The ACS a 20-item self-report instrument in the NIH Toolbox⁶⁶ that measures participants' perceived ability to (a) focus on relevant stimuli while ignoring distractors (e.g., "My concentration is good even if there is music in the room around me"), and (b) shift attention (e.g., "After being interrupted or distracted, I can easily shift my attention back to what I was doing before"). The ACS will be administered at the clinical assessment visits (baseline, mid-treatment, post-treatment, and 3-month follow-up) as well as weekly during the therapy visits.

Attentional Engagement-Disengagement Task (AEDT)⁴⁰: The AEDT will be used as a behavioral measure of attentional control. Two emotional faces are presented (happy, disgusted, and sad paired with neutral faces; Radboud Faces database)⁶⁷ and eye tracking is measured; 72 trials. Half of trials measure (a) *attentional engagement* with emotional expressions (i.e., once participants fixate on the neutral face, a frame around the emotional face indicates they should shift their gaze), and the other half measure (b) *attentional disengagement* (i.e., shifting from emotional to neutral). Gaze latency (i.e., time to fixation) is the main outcome. This task has been linked to rumination⁶⁸ and is sensitive to treatment.⁶⁹ It is expected that individuals with RNT will display delayed disengagement (i.e., longer time to fixation) when shifting from negative to neutral stimuli (vs. from positive to neutral or from neutral to emotional)³⁷⁻³⁹, which is expected to improve with ERT-AR. Eye movements will be recorded using a Tobii Pro X3-120 (described in "Equipment" below). The AEDT will be administered at the following timepoints: baseline (week 0), mid-treatment (week 4), and post-treatment (week 8). Computer task sessions will occur within a 7-10-day window, but no longer than 14 days from each clinical assessment visit.

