Patient Feedback Questionnaire: This questionnaire allows participants to provide feedback on their experience during treatment, including general satisfaction with their treatment condition and treatment length, which aspects of therapy they found most confusing or most helpful, and usefulness of the therapy website and forms. This self-report questionnaire will be administered at post-treatment only.

After ART Usage and Additional Treatment Form: This self-report form asks participants to report their usage and the usefulness of the study website, and probes for the need for additional treatment at the 3-month follow up assessment.

Equipment

Eye-tracking data will be collected during the AEDT and EIT tasks. The eye tracking equipment will be located in a dedicated office within the OCD Program. We will use a Tobii Pro X3-120 screen-based eye tracker (The Tobii Group, Danderyd, Sweden) which samples eye-

gaze coordinates at 120 Hz. Eye tracking data will be transmitted via USB 3.0 to a LAN with External Processing Unit and converted to visual fixation data using the iMotions Biometric Research Platform (Boston, MA, USA).

The electroencephalogram (EEG) equipment is located at the MGH Martinos Center (Charlestown, MA). EEG data will be acquired using BrainVision software (Brain Products GmbH, Gilching, Germany) that is installed in a dedicated behavioral testing laboratory. The EEG amplifier is an actiCHamp active amplification system (24-bit battery, up to 1000 Hz sampling rate). It is used with actiCAP EEG caps, which are fitted with 32-electrode modules. Our system is configured for use with 96 electrodes (3 modules) to provide dense scalp coverage, which is helpful for spatially localizing event related potentials (ERPs) and is necessary for accurate source localization. The cap can be fit to a participant in about 30 minutes to provide an individualized and comfortable fit for each person. The actiCHamp system uses active electrodes and gel to minimize impedance and maximize signal-to-noise ratio (SNR); impedances will be kept under 30 kOhms to ensure high SNR. The N2 and N450 ERP components will be measured at midline frontal (Fz) and central (Cz) sites, while the P300 will be measured at a midline parietal site (Pz). Digitization of three-dimensional electrode positions will be accomplished via the BrainVision CapTrak system. Data processing and analysis will occur offline using BrainVision Analyzer 2.0 and MatLab (Natick, MA, USA).

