Our multi-level generalized linear modeling (GLM) approach (described below under “Primary Analyses”) uses an intent-to-treat analysis that includes all participants, regardless of missing data (increasing power and generalizability), and it provides accurate estimates of regression coefficients in small samples.^{118,119} Despite our best efforts to retain participants, we do expect dropouts (i.e., subjects who are lost to follow-up or withdraw early from the study for reasons described below under “Participant Withdrawal”). We will attempt to perform all scheduled assessments for subjects who are withdrawn from the protocol and will provide financial incentives for participation in assessments.

Missing data rates and patterns will be assessed by treatment arm. Reason(s) for missing data will be documented, and we will evaluate reasons for dropout, study withdrawal, and loss-to-follow-up by treatment group. We will attempt to ascertain if missingness is occurring at random by evaluating factors associated with dropout for potential attrition bias. We will also compare study dropouts to study completers on demographic and clinical variables. Finally, we will use sensitivity analyses to quantify the impact of missing data.¹²⁰

Data Processing

For behavioral tasks that include reaction times (e.g., the Emotional Interference Task [EIT]), we will remove reaction times <150 ms given that such responses are rare and likely represent errors.¹²¹ Eye position fixations from the Attentional Engagement-Disengagement Task (AEDT) sampled at 120Hz will be converted to visual fixation data using standard criteria (i.e., minimum duration 100ms; minimum radius 1 degree).¹²²

Eye-blink artifacts will be removed from scalp-recorded EEG data on the Cued

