Emotional Control Task (CECT) and during the resting-state period (0.1-100Hz, sample rate = 256Hz) using established procedures,¹²³ and gross artifacts will be rejected by visual inspection. For the CECT, cue- and target-locked event related potentials (ERPs) will be formed by segmenting EEG data around cue and stimulus onsets (from -200 ms to 1000 ms post-stimulus) and averaging the segments. Start and end points for the components of interest are: (a) cue-locked N2: 200-350ms post-cue; (b) target-locked N2: 200-350ms post-target; (c) target-locked N450: 400-500ms post-target; (d) target-locked P300: 300-600ms post-target.⁴⁹ ERPs will be rejected if there is significant artifact (e.g., amplitude $\pm 100 \mu\text{V}$) at any electrode on a given trial. Artifact-free mean amplitudes (μV) will be extracted for ERP analyses. Additionally, nonoverlapping, artifact-free 2-second epochs from the resting-state period will be extracted for source localization analyses. Building on recent source localization studies,^{80,124} seeds from key regions within the frontoparietal (FPN) and default mode (DMN) networks will be selected to create regions of interest (ROIs) based on previous published methods^{125,126} and drawing from the Montreal Neurological Institute 305 template.¹²⁷ We will then compute EEG source-based functional connectivity using exact Low Resolution Electromagnetic Tomography (eLORETA) software.⁷⁸

Primary Analyses

Due to the nested structure of the data (i.e., 4 assessments per participant), we will use a multi-level generalized linear modeling (GLM) approach to address each of our hypotheses.

Hypothesis 1: Target Engagement. To test whether participants who receive AR-ERT show greater improvements in attentional/cognitive control relative to those who receive SPT, we will run a series of GLM analyses for each index of our attentional/cognitive control target:

- 1) **Behavioral:** (a) attentional disengagement (i.e., latency of shift in gaze from emotional to neutral face surrounded by the frame; AEDT), and (b) sustained attention (i.e., difference in reaction times to tones following a negative vs. neutral stimulus on the EIT),

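### The fixation rule for the AEDT sets a lower limit on gaze spread where stable gaze needs an upper one; it is probably a wording slip, but as written it would make the disengagement latency unusable

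*Combined protocol and SAP*

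**What the plan says.** The rule is in section 6, Data Processing, and covers the AEDT gaze recordings. Fixations are to be detected from them under "standard criteria (i.e., minimum duration 100ms; minimum radius 1 degree". A general eye-tracking methods text is cited for it.

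The Equipment part of section 5 describes a screen-based tracker that records "gaze coordinates at 120 Hz" and says the data are "converted to visual fixation data using the iMotions Biometric Research Platform". It gives no algorithm, velocity threshold, dispersion limit or software setting.

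Two places show what depends on the rule:

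- The AEDT description in section 5 says "Gaze latency (i.e., time to fixation) is the main outcome".
- Section 6, Primary Analyses, Hypothesis 1, makes the first behavioural index attentional disengagement, defined as "latency of shift in gaze from emotional to neutral face surrounded by the frame; AEDT". Hypothesis 2b then correlates pre-to-post change in the AEDT with change in the clinical measures.

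**The concern.** Duration and spread are bounded from opposite sides in any definition of a fixation as stable gaze. The eye must stay long enough (a lower limit on time) and within a small enough area (an upper limit on spread). The plan puts a lower limit on both. Under that rule, the steadier the gaze, the more surely the fixation is thrown out, while a run of samples that scatters or sweeps across a degree or more qualifies.

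The AEDT score is a time to fixation. If the looks that should stop the clock are discarded, a trial has no latency, or it is timed from a noisy or moving stretch of gaze. An analyst who follows the plan would get unusable latencies. One who departs from it, sensibly, makes a choice that the plan does not record. Either way, the index cannot be reproduced from the plan as it stands.

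**Working it through.** The plan states no figure that can be reproduced here, since the point concerns the direction of a threshold. The check has three parts.

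**1. Is the rule corrected anywhere?** The places that bear on it are Data Processing (section 6), Equipment and the AEDT description (section 5), and Hypothesis 1 (section 6). Only Data Processing gives a spatial criterion. None of the others defines radius, names an algorithm or gives a maximum spread.

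**2. What would the literal rule do?** Inputs:

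- From the plan: 120 Hz, 100 ms, 1 degree. Window length is 0.100 s × 120 per s = 12 samples.
- Assumed: independent Gaussian gaze scatter around one fixed point, SD σ per axis. The plan gives no value, so a range is shown.
- Assumed: radius is the largest distance of any sample from the window's centroid, R = max over i of √[(xᵢ − x̄)² + (yᵢ − ȳ)²].

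Share of steady windows with R ≥ 1 degree, that is, accepted under the literal rule (30,000 simulated windows per cell):

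| σ (degrees) | 12 samples (100 ms) | 24 samples (200 ms) | 36 samples (300 ms) |
|---|---|---|---|
| 0.1 | 0% | 0% | 0% |
| 0.2 | 0% | 0% | 0.02% |
| 0.3 | 3% | 7% | 11% |
| 0.4 | 33% | 61% | 77% |
| 0.5 | 75% | 96% | 99% |
| 0.75 | over 99% | 100% | 100% |

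A closed-form approximation, treating the n distances as independent, is P(R ≥ 1) ≈ 1 − [1 − exp(−1 / (2σ²(1 − 1/n)))]ⁿ. For σ = 0.4 and n = 12, the exponent is −1 / (2 × 0.16 × 11/12) = −3.41, so exp(−3.41) = 0.033 and 1 − (1 − 0.033)¹² = 0.33. This agrees with the simulated 33%.

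A maximum-radius rule keeps the complement. For 12 samples that is 100% at σ up to 0.2, 97% at 0.3, 67% at 0.4 and 25% at 0.5. The two shares sum to 100% by construction, so the second column of evidence adds nothing independent; what matters is which way acceptance moves with σ. A simulated 8-degree sweep completed within 100 ms (σ = 0.1) was accepted by the literal rule every time and by the maximum rule never.

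**Sensitivity to the definition.** If radius means the root-mean-square distance from the centroid, the literal rule with 12 samples accepts about 0% of steady windows up to σ = 0.5 and 50% at σ = 0.75. The direction is the same, but the size is very different.

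**3. How far does it reach?** Hypothesis 1 lists seven indices: AEDT disengagement latency, EIT interference, cue-locked N2, target-locked N2, N450, P300 and the ACS. Only the first uses this rule. The EIT index is a button-press reaction time; the ERPs and the ACS do not involve gaze. The PTQ-PW, named as the primary outcome, is a self-report scale.

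**The case against.** The strongest reply is that this is one wrong word. The plan calls the criteria standard, cites a methods text and leaves the conversion to commercial software, so the settings actually used may well be conventional. That stands: nothing in the document shows a minimum-spread filter being run.

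A second reply is that radius is undefined. The phrase could mean the least distance gaze must move before a new fixation is counted, which would act much like a maximum spread. The document does not exclude this. But if the text supports two readings with opposite effects, it does not specify one rule, so the reply limits the charge without removing it.

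Third, at low scatter the literal rule would return almost no fixations. Section 6 (Overview) calls for descriptive statistics and graphs for every measure, so a nearly empty AEDT file would be hard to miss. That is fair, and it makes silent bias less likely than an obvious failure. The rule also applies alike to both arms, and no effect on the week 8 treatment contrast has been estimated.

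A reader might be tempted to go further in three ways that the documents do not support:

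- **That the latencies are already wrong or missing.** This would require evidence of how sessions were processed, and there is none.
- **That the surviving trials would come from poorly calibrated recordings.** The simulation varies random scatter about a centroid, which is precision. A constant calibration offset leaves R unchanged.
- **That the rule also governs the trial itself, because the frame appears** "once participants fixate on the neutral face, a frame around the emotional face indicates they should shift their gaze". Data Processing describes conversion of recorded data, and nothing says the in-task trigger uses the same criterion.

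**Conclusion.** The criterion is wrong as worded and should be corrected. It is the operative rule in the analysis section for an index of the primary aim, and no other text overrides it. If it were applied literally, with radius as a measure of spread, the AEDT disengagement latency would be unusable, and so would the Hypothesis 2b correlations that use it.

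The conclusion on direction needs only the meaning of a fixation as stable gaze. The percentages need more: an assumed scatter, independent Gaussian noise and one definition of radius. They are illustrations, not estimates for this trial.

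The damage is confined to one of seven Hypothesis 1 indices and is conditional on the rule having been run as written. It would be going too far to infer that the primary aim as a whole or the PTQ-PW result is compromised.

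**What to change.** Restate the spatial criterion in section 6, Data Processing, with the threshold in the right direction. For a dispersion-type rule: a fixation is a run of gaze samples lasting at least 100 ms (12 samples at 120 Hz) that stays within a maximum radius of 1 degree. Define radius, for example as the largest distance from the centroid. If the software uses another type of algorithm, name it and give its threshold instead.

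Then confirm from the iMotions settings that the same rule was used for every AEDT session, and re-export any session processed otherwise before unblinded analysis.

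The cost is a sentence in the plan and a check of export settings. No new data are needed.
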